1.3 Schedule of Activities

The schedule of activities (SoA) planned in this study are presented in [Table 1](#).

Table 1 Schedule of Activities

Assessment/Procedure	Inclusion Visit[a] Day 1			Follow-Up Visits Every 6 months (± 1 month)[b]/ EOS/EW Visit[c]	
	Procedures already performed at the parent EOS Visit that will be transferred from parent study database	Procedures already performed at the parent EOS Visit to be entered in CLIN-60120-452 eCRF by the study site	Procedures to be performed at the CLIN-60120-452 Inclusion Visit	In-clinic Visit	Remote visit
Informed consent[d]			X		
Inclusion/exclusion criteria			X		
Study intervention administration/accountability[e]			X	X	X
Baseline demographics			X		
Physical examination			X		
Participant interview[f]			X		
Pregnancy testing and childbearing potential [g]		X[a]*		X	X
Linear height and body weight [h]		X[a]*		X	X
Vital signs [i]		X[a]*		X	X
Spinal health assessment [j]		X [a]**		X	
Lung function assessments [k]			X	X	
Flare-up assessment [l]			X	X	X [m]
Additional Extra bone growth assessment (without associated flare-up)			X	X	X
CAJIS [n]	X*			X	X
C-SSRS [n] [o]			X	X	X
FOP-PFQ assessment[p] [q]	X*		X [q]***	X	X
PROMIS Global Health Scale [p][q]	X*		X [q]***	X	X
FOP assistive devices assessment [p]			X	X	X
Healthcare Utilization [p]			X	X	X
Biochemistry (amylase, lipase, AST, ALT) and triglycerides	X*				
Disease and flare-up history	X				
Prior medications	X				
Concomitant medications		X		X	X
Concomitant procedures [r]		X		X	X
AEs [s]		X		X	X

AE=adverse event; ALT=alanine aminotransferase; AST=aspartate aminotransferase; CAJIS=Cumulative Analogue Joint Involvement Scale for FOP; COVID-19=coronavirus disease 2019; C-SSRS=Columbia-Suicide Severity Rating Scale; DLCO=diffusion capacity of the lung for carbon monoxide; eCRF=electronic case report form; EOS=End of Study; EW=Early Withdrawal; FEV₁=forced expiratory volume in one second; FVC=forced vital capacity; FOP=fibrodysplasia ossificans progressiva; FOP-PFQ=FOP Physical Function Questionnaire; PROMIS=Patient Reported Outcomes Measurement Information System.

a. The Inclusion Visit should be in-clinic and corresponds ideally to the EOS Visit of the parent study (Study PVO-1A-301 or PVO-1A-202/PVO-1A-204). A maximum of one month is allowed between the two visits. For any assessments

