from the parent EOS Visit performed outside this allowed time window, assessments will need to be performed again at the Study CLIN-60120-452 Inclusion Visit (flagged with *). However, to enable continued access to the Investigational Product and rollover of participants with impaired mobility [in the case(s) when per investigator's judgement this is considered as beneficial for the participant's medical conditions], the parent EOS Visit and consenting for CLIN-60120-452 and CLIN-60120-452 Inclusion Visit can be conducted remotely. In such case(s) both parts of remote consenting used by the site – i.e. Informing/Consenting discussion and ICF signature should be agreed with the IRB/EC, and the investigator's judgement should be sufficiently documented in the patient source notes.

For the spinal health assessment, a time window of 3 months post parent visit is allowed (flagged with **).

- b. Follow-up Visits will be either in-clinic or performed remotely (e.g. at the participant's home by qualified SP in-home services, and/or via video-conference or telephone contact from clinical site personnel).
- c. The EOS/EW Visit will be ideally an in-clinic visit (or remotely when permitted by the IRB/IEC) and will occur at the time of last study intervention intake. The EOS Visit must take place before the participant transitions to commercial treatment.
- d. For participants <18 years, assent and legal guardian's consent will also be required.
- e. Palovarotene status (treated or not treated) and regimen (chronic or flare-up treatment) at the time of transition to Study CLIN-60120-452 will be collected at the Inclusion Visit. Participants will be supplied with chronic treatment as well as the appropriate dose of palovarotene to initiate flare-up treatment when a flare-up or traumatic event is confirmed by the investigator. Participants will be instructed to report potential flare-up symptoms to study site personnel, only one symptom is required to define a flare-up (see Section 6.1). In the presence of persistent flare-up symptoms, treatment may be extended in 4-week intervals until the flare-up symptoms resolve. If the participant experiences an intercurrent flare-up, or substantial high-risk traumatic event likely to lead to a flare-up, at any time during the flare-up treatment, the 12-week flare-up treatment should be restarted.

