Participants will continue to receive palovarotene until it is reimbursed in the country where the study is being conducted, or another access programme becomes available, or until the study end date of November 2024 is reached, whichever occurs first. At this time, investigational palovarotene will be discontinued to allow participants to transition to the commercially available drug, physician-prescribed palovarotene, or to another access programme, if available. Early access can only take place if it is allowed within the local laws, rules and regulations or specifically approved in writing by local authorities.

Participants can voluntarily withdraw from the study at any time for any reason.

The study intervention can be discontinued for individual participants by the investigator if he/she believes the participants' safety is at risk.

In the event of early study withdrawal or early discontinuation of the study intervention, all reasonable efforts should be made by the study personnel in-clinic or remotely to have the participants complete all study assessments of the EW Visit as per the SoA.

Participants will be followed-up in-clinic or remotely for safety for 30 days after the last palovarotene dose of the study is received. If the study intervention was discontinued due to a safety concern, the participant will be monitored for safety (see [Section 8.3.3](#) for follow-up of AEs/serious adverse events (SAEs) and [Section 8.3.5](#) for follow-up of pregnancies).

The EOS for an individual participant will be the date of study completion due to palovarotene becoming reimbursed in the country where the study is being conducted, or another access programme becoming available, or the study end date of November 2024 being reached, whichever occurs first.

The maximum duration of the study is three years from enrolment to last study visit (November 2021 to November 2024).

An Independent Data Monitoring Committee (IDMC) will be set-up, as described in [Section 10.1.5](#).

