8.3.1 Time Period and Frequency for Collecting AE and SAE Information

All AEs (including SAEs) will be collected from the signing of the ICF until last study intervention intake + 30 days at the time points specified in the SoA (Table 1).

All AEs that first occurred during participation in the parent study and are ongoing at the time of transition to Study CLIN-60120-452 will be collected and entered again as ongoing AEs/SAEs in the Study CLIN-60120-452 eCRF at the signing of the ICF.

All SAEs will be recorded and reported to the sponsor or designee immediately and under no circumstance should this exceed 24 hours of awareness of the event, as indicated in Section 10.3. The investigator will submit any updated SAE data to the sponsor within 24 hours of it being available.

Investigators are not obligated to actively seek information on AEs or SAEs after conclusion of the study participation (unless any AEs/SAEs or their sequelae persist after this date, follow-up is required until the event or its sequelae resolve or stabilise, or the participant is lost to follow-up). However, if the investigator learns of any SAE, at any time after a participant has been discharged from the study, and he/she considers the event to be reasonably related to the study intervention or study participation, the investigator must promptly notify the sponsor (through pharmacovigilance).

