9.4.2 Analysis of Primary Endpoint

The primary endpoint is the incidence and description of all TEAEs, serious and nonserious treatment-related TEAEs, all serious TEAEs and all nonserious TEAEs.

A TEAE is defined as any AE that occurs after signing the ICF of Study CLIN-60120-452 or an ongoing AE from the parent study with a worsening in severity or relationship to the study intervention following transition to Study CLIN-60120-452.

Ongoing AEs from the parent study with no change in severity or relationship to the study intervention following transition to Study CLIN-60120-452 will not be considered TEAEs.

Any event that first occurred during participation in the parent study and is ongoing at the time of transition to Study CLIN-60120-452 will therefore be a (non-TEAE) AE.

All ongoing AEs from the parent study and all TEAEs that occur following the signing of the ICF until last study intervention intake + 30 days will be included in the participant data listings using the Full Analysis Set (FAS)/Safety Set. Primary endpoint analyses and summary tables will be presented by parent study, by palovarotene status at the time of transition to Study CLIN-60120-452 and treatment regimen and overall for the FAS/Safety Set.

Adverse events/TEAEs will be coded according to Medical Dictionary for Regulatory Activities (MedDRA) and will be classified by PT and SOC. Adverse events/TEAE listings will be presented by participant, SOC and PT.

The incidence of all reported TEAEs, serious and nonserious treatment-related TEAEs, all serious TEAEs, all nonserious TEAEs, TEAEs leading to death and TEAEs leading to treatment discontinuation will be tabulated separately. In addition, summary tables for TEAEs will be presented by maximum intensity and study intervention relationship (investigator-reported causality assessment).

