### 5.7.2.2 Primary Analysis – Adverse Events

All adverse events (AEs) recorded in the eCRF will be coded using the latest version of MedDRA dictionary at the time of the database lock and will be classified by System Organ Class (SOC) and Preferred Term (PT). [Note: All ongoing AEs at the time of participant transition will be transferred from the parent study database]

AEs will be classified as Treatment-Emergent AEs (TEAEs) according to the rules below:

- Events with start date on or after the date of first IMP administration and up to 30 days after date of last dose of treatment of palovarotene in Study CLIN-60120-452 (or date of last contact if not available).

- Ongoing AEs from the parent study with a worsening in intensity or relationship (see relationship and intensity order below) to the study intervention following transition to Study CLIN-60120-452. New AEs during Study CLIN-60120-452 will be compared by SOC and PT to all previous study ongoing AEs for comparison of the intensity and relationship.

Ongoing AEs from the parent study with no change in intensity or relationship to the study intervention following transition to Study CLIN-60120-452 will therefore be an AE (non-TEAE).

In the case where it is not possible to define an AE as treatment emergent or not, the AE will be classified by the most conservative case; i.e. treatment emergent.

The below summaries will be provided:

- An overview table summarising the:
  - number and percentage of participants with at least one of the following AEs: any AE; any TEAE; maximum intensity of TEAEs; causality of TEAEs, worst causality and intensity of TEAEs (worst case); TEAE leading to a dose change; TEAE leading to withdrawal; TEAE leading to death; Serious Adverse Events (SAEs); Serious TEAE;
  - corresponding number of events for each of the AE categories listed above
- A summary of the number and percentage of participants reporting an AE by SOC and PT
- A summary of the number and percentage of participants reporting a TEAE by SOC and PT
- A summary of the number and percentage of participants reporting a TEAE by maximum intensity, SOC and PT
- A summary of the number and percentage of participants reporting a TEAE by worst causality, SOC and PT
- A summary of the number and percentage of participants reporting a related TEAE by SOC and PT
- A summary of the number and percentage of participants reporting a TEAE by intensity, causality, SOC and PT

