- A summary of the number and percentage of participants reporting a non-Serious TEAE by SOC and PT
- A summary of the number and percentage of participants reporting a non-Serious related TEAE by SOC and PT
- A summary of the number and percentage of participants reporting a TEAE leading to treatment discontinuation by SOC and PT
- A summary of the number and percentage of participants reporting a TEAE leading to dose change (increase or decrease) by SOC and PT

The below summaries will also be provided by treatment dose at time of AE onset (5mg, 10/20mg and all palovarotene):

- Overall summary of Adverse events
- A summary of the number and percentage of participants reporting a TEAE by SOC and PT

- A summary of the number and percentage of participants reporting a TEAE by maximum intensity, SOC and PT
- A summary of the number and percentage of participants reporting a TEAE by worst causality, SOC and PT
- A summary of the number and percentage of participants reporting a TEAE leading to treatment discontinuation by SOC and PT
- A summary of the number and percentage of participants reporting a TEAE leading to dose change (increase or decrease) by SOC and PT

To calculate the treatment regimen at time of AE onset, the start date of each AE will be merged with each participant dosing log. Given dosing end dates are not captured the latest dosing record prior to the AE start date will be identified. If the dosing record is either 0 mg or after treatment discontinuation the regimen will be set to “off treatment”.

AEs will be counted as follows:

- AEs summaries will be ordered in terms of decreasing frequency for SOC and PT within the overall column of each output.
- Participants with more than one AE within a particular SOC are counted only once for that SOC. Similarly, participants with more than one AE within a particular PT are counted only once for that PT.
- Participants reporting a TEAE more than once within that SOC/ PT, the TEAE with the worst-case intensity (intensity order: severe > missing > moderate > mild) will be used in the corresponding intensity summaries.
- Participants reporting a TEAE more than once within that SOC/ PT, the TEAE with the worst-case causality to study medication (order: related > missing > not related) will be used in the corresponding relationship summaries;

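### The promised 30-day follow-up after the last dose has no AE time point in the Schedule of Activities, so the end of the TEAE window risks under-ascertainment

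*Protocol*

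**What the plan says.** **Collection rule.** Protocol 8.3.1 has AEs and SAEs "collected from the signing of the ICF until last study intervention intake + 30 days at the time points specified in the SoA". Table 1 marks the AE row at Inclusion and in the combined Follow-up/EOS/EW columns, and nowhere later. Footnote c says that the EOS/EW Visit "will occur at the time of last study intervention intake".

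**Follow-up promise.** Section 4.1 states: "Participants will be followed-up in-clinic or remotely for safety for 30 days after the last palovarotene dose of the study is received". The synopsis (1.1) says the same. Neither gives a day, a procedure or a form.

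**Other post-dose provisions.** Table 1 footnote g and Section 8.2.6 require a pregnancy test one month after stopping, with the result in the eCRF. It concerns females only, and 8.2.6 allows it to be self-administered. Section 8.3.3 follows AEs that have already been reported.

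**End of participation.** Section 8.3.1 releases investigators from actively seeking AEs once participation has concluded, apart from persisting events, without saying when that is. Section 4.4 regards a participant as having completed the study once study drug stops for one of the listed access or end-date reasons.

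**Analysis window.** Protocol 9.4.2 covers "all TEAEs that occur following the signing of the ICF until last study intervention intake + 30 days". SAP 5.7.2.2 counts events "up to 30 days after date of last dose of treatment of palovarotene in Study CLIN-60120-452".

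**Label after the last dose.** For dose at AE onset, SAP 5.7.2.2 says: "If the dosing record is either 0 mg or after treatment discontinuation the regimen will be set to" off treatment. Protocol 4.1 says that at the end of a participant's study treatment "investigational palovarotene will be discontinued to allow participants to transition to the commercially available drug", or to another access programme if there is one.

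**The concern.** TEAE incidence is the primary endpoint, and its window ends 30 days after the last AE time point in the schedule. Sites work from the schedule. If it shows nothing after the EOS/EW Visit, whether anyone asks about new AEs in that month depends on how each site reads Section 4.1. Non-serious events are the most exposed, because 8.3.1 keeps a duty to report SAEs considered related whenever the investigator learns of them.

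The period is not a trivial one for safety. Section 8.2.2 asks for close observation for suicidal ideation and behaviour especially at the beginning and end of the course, yet the C-SSRS row also ends at the EOS/EW Visit.

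A secondary issue concerns participants who move to non-study palovarotene after their last study dose. An AE that starts after the move would begin on drug but be labelled as off treatment in the tables by dose at onset.

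**Working it through.** The plan gives no figure to reproduce. The check sets the passages side by side and then sizes the interval.

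**1. End of window against last AE time point**

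| Item | Time | Source |
|---|---|---|
| End of AE collection | last dose + 30 days | Protocol 8.3.1 |
| End of TEAE window | last dose + 30 days | Protocol 9.4.2; SAP 5.7.2.2 |
| Last AE time point in Table 1 | last dose + 0 days | AE row; footnote c |

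Difference: 30 − 0 = 30 days for which 8.3.1 refers to time points that Table 1 does not contain.

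**2. Does other text supply the AE contact?**

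- Sections 1.1 and 4.1 require follow-up but specify no AE contact.
- The one-month pregnancy test need not involve an AE enquiry, and males have no such test.
- Section 8.3.3 covers events already reported. The extra monitoring in Section 7.1 applies only where treatment was permanently discontinued for a safety concern.
- If completion under 4.4 is read as the conclusion of participation in 8.3.1, the duty to ask can lapse on the day of the last dose. That conflicts with 4.1 and with the first sentence of 8.3.1. The text does not settle which reading applies.

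**3. Share of the window in calendar time**

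Actual treatment durations are not given. The scheduled days in SAP 6.1 serve as illustrative treatment durations T, and the share is 30 / (T + 30).

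| T (days) | Approximate duration | Calculation | Share |
|---|---|---|---|
| 182 | 6 months | 30/212 | 14.2% |
| 365 | 12 months | 30/395 | 7.6% |
| 730 | 24 months | 30/760 | 3.9% |
| 1095 | 36 months | 30/1125 | 2.7% |

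**4. Study end date**

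Section 4.1 has the last study visit in November 2024. A last dose on 1 November + 30 days gives 1 December, and one on 30 November gives 30 December. Any last dose in that month has a window that closes after the stated end. SAP 3.3 runs the final analysis once all participants have completed the study, which under 4.4 can be before the window closes.

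**5. Knock-on effect of adding a contact**

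SAP 5.8.2 ends the last dosing period at the recorded last dose, with the date of last contact as fallback. SAP 5.8.2.1 sets the last dose date to the date of last contact, and 5.8.2 takes that as the latest date across all assessments. Under 5.8.2.1 as written, a contact at day 30 would add up to 30 days to total treatment duration.

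**6. Off-treatment label**

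The by-dose tables in SAP 5.7.2.2 list 5 mg, 10/20 mg and all palovarotene. None of these columns is for events labelled off treatment, and the supply taken after the last study dose is not considered.

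**The case against.** The strongest reply is that the protocol does require follow-up. Sections 1.1 and 4.1 say so, 8.3.2 prefers open-ended questioning about AEs, and 8.3.1 itself sets the period at + 30 days. On this view a line is missing from a table and nothing is missing from the design. This stands in part, and it rules out several stronger readings that a reader might infer:

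- *There is no contact after the last dose.* Sections 1.1, 4.1 and footnote g contradict this. What is missing is a defined AE time point.
- *Late AEs are captured only if volunteered.* This holds only if participation concludes at the last dose, which is one reading of an ambiguous text.
- *The SAP treats the window as fully observed.* The SAP includes the window without adjustment but makes no such claim. The AE summaries it lists are counts and percentages, not rates over person-time.
- *The percentages measure missed events.* They are shares of calendar time. A participant who already has a TEAE counts in overall incidence whatever happens later.
- *Every participant is affected alike.* Participants on the flare-up-only regimen, or with interrupted dosing, may have a later visit that covers part of the window.
- *The off-treatment label distorts the primary incidence.* It bears only on the tables by dose at onset and can be read as off study treatment. Section 4.1 gives no timing for a move to other supply.

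Protocol Section 10.3, to which 8.3 refers for recording procedures, and the study schema figure were not in the text available for review. Either might add detail. The mismatch between 8.3.1 and Table 1 would remain, because 8.3.1 names that schedule as the source of its time points.

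**Conclusion.** The point holds as an inconsistency within the protocol that bears on the primary endpoint. Sections 1.1 and 4.1 require a 30-day safety follow-up, the analysis counts events through it, and the schedule that 8.3.1 relies on contains no AE time point for it. The consequence is a risk of under-ascertainment of TEAEs in that interval. Its size cannot be derived from the documents. The 2.7% to 14.2% of the window in calendar time shows the extent of the interval only, and it rests on illustrative treatment durations of 36 to 6 months and on the EOS/EW Visit falling at the last intake, as footnote c states. The off-treatment label is a secondary matter confined to the by-dose tables. The correction is worth making because it is small and carries out what 4.1 already requires.

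**What to change.** 1. **Table 1 and Section 8.3.1.** Reconcile them with 1.1 and 4.1 by adding one remote contact at last study dose + 30 days. It records AEs, concomitant medication and the start date of any non-study palovarotene.
2. **Timing.** State that conclusion of participation (8.3.1), last participant last visit and database lock fall after this contact. Section 4.4 already defines study end by the last contact with the last participant, so the main change is to participant completion and the database lock.
3. **SAP 5.8.2.1.** Use the recorded last dose date, as 5.8.2 does, and not the date of last contact. Without this, item 1 would inflate exposure.
4. **SAP 5.7.2.2 (secondary).** In the tables by dose at onset, label AEs after the last study dose as non-study palovarotene or off treatment, according to the recorded supply, and say where they are shown.

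Cost: one telephone contact per participant (at most 87), one column in Table 1 and short SAP edits. The last contacts would fall up to 30 days after the last study dose in November 2024, so the stated end date needs matching wording.
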